5.1.4. Optional Part D (Pharmacokinetics of Capsule and Tablet Formulations and Food Effect)

The decision to conduct Part D will be made after review of safety, tolerability, and PK data from Parts A (SAD) and B (CYP3A4 Inhibition). Part D may be conducted in parallel with Part C.

Part D is optional and will assess the PK of single oral doses of LY3154885 in approximately 9 healthy subjects when administered as a capsule (Period 1), as a tablet (Period 2), and as a tablet with a high-fat diet (Period 3). The dose for Part D will not exceed the highest dose tested in Part A (SAD) that was deemed safe and well tolerated.

In Periods 1 and 2, subjects will be admitted to the CRU the afternoon of Day -2 for set up of baseline ABPM (see Section 9.4.4); admission for Period 3 will be on Day -1. In Period 1, subjects will undergo an overnight fast (see Section 6.3.1) before receiving a single oral dose of

LY3154885 (capsule formulation) on Day 1. Subjects will remain inpatient for at least 48 hours after dosing, after which they may be discharged at the discretion of the investigator. Subjects will be re-admitted to the CRU on Day 6 and will undergo an overnight fast before receiving a subsequent single oral dose of LY3154885 on Day 8 with the same formulation. Subjects will be discharged on Day 10, at least 48 hours after dosing. Re-admission to the CRU will be on Day 13, and following an overnight fast, subjects will receive a single oral dose of LY3154885 on Day 14 with the same formulation. Final discharge from the CRU will occur on Day 16. Pharmacokinetic sampling will be conducted as detailed in the Schedule of Activities (Section 2).

Period 2 will be conducted as described for Period 1; however, LY3154885 will be administered as a tablet formulation.

Period 3 will be conducted as described for Period 1; however, subjects will receive a single oral dose of LY3154885 (tablet formulation) after administration of a high-fat diet (see Section 6.3.1).

The follow-up visit will occur approximately 7 days after final discharge.

Figure HUAA.5.4 illustrates the study design for Part D.

	Period 1		Period 2		Period 3	
LY3154885 n=9	LY3154885 capsule (Days 1, 8 and 14)	≥7 day washout	LY3154885 tablet (Days 1, 8 and 14)	≥7 day washout	LY3154885 tablet after high fat meal (Days 1, 8 and 14)	≥7 day washout

Intensive PK sampling on Days 1, 8, and 14

Abbreviation: n = number of subjects; PK = pharmacokinetic.

Figure HUAA.5.4. Illustration of study design for Part D.

5.2. Number of Participants

For Part A, up to 30 subjects may be enrolled into Cohorts 1 and 2 in order to ensure that approximately 12 subjects per cohort (8 LY3154885; 4 placebo) complete this part of the study.

For Part B, up to 15 subjects may be enrolled in order to ensure that approximately 12 subjects (9 LY3154885; 3 placebo) complete this part of the study.

For Part C, up to 45 subjects may be enrolled in order to ensure that approximately 36 subjects complete this part of the study (with approximately 12 subjects [9 LY3154885; 3 placebo] completing each dose level).

For optional Part D, up to 12 subjects may be enrolled in order to ensure that approximately 9 subjects complete this part of the study.

5.3. End of Study Definition

End of the study is the date of the last visit or last scheduled procedure shown in the Schedule of Activities (Section 2) for the last subject.

5.4. Scientific Rationale for Study Design

This study will be conducted to evaluate the safety, tolerability, and PK of single and multiple doses of LY3154885 in healthy subjects.

In Parts A, B, and C, the subjects and site staff (except pharmacy staff) will be blinded to treatment allocation to allow an unbiased assessment of the safety and tolerability data, which will allow a more robust comparison between LY3154885 and placebo data.

In Part A, B, and D, a washout period of at least 7 days has been selected to minimize carryover effects between doses based on the predicted human PK of LY3154885 from nonclinical studies.

[figure not shown]
A tablet formulation is being developed for upcoming studies and the effect of food on the PK of LY3154885 is unknown; therefore, Part D will compare the PK profile of a tablet formulation versus capsule formulation and the effect of food on the PK of LY3154885 given with the tablet formulation.

5.5. Justification for Dose

In Part A, the planned clinical doses to be tested are 15, 45, 100, 200, 400, and 500 mg based on animal toxicology/toxicokinetics, preclinical pharmacology, and PK information. In Part B (CYP3A4 Interaction), the LY3154885 dose selection will be based on emerging data from Part A but is currently planned to be \leq 200 mg. In Part C (MAD), dose selection will be based on emerging safety, tolerability, and PK data from Part A and Part B, but Part C is currently planned to start at 35 mg and not exceed the highest dose in Part A or the maximum exposure achieved in Part A or B that are found to be well tolerated. In Part D, the dose for the capsule and tablet is planned to be \leq 400 mg but will ultimately be based on emerging safety, tolerability, and PK data from Part A.

The toxicity profile of LY3154885 has been characterized in rats and monkeys through a package of GLP compliant, repeat-dose toxicology, safety pharmacology, and genetic toxicology studies; non-GLP toxicity studies were conducted with LY3154885 as well and are discussed in the IB. These studies with LY3154885 demonstrate an acceptable safety profile for human testing with CV and CNS effects that are transient and monitorable.

CCI

CCI

(Table HUAA.5.1).

The maximum dose for this study is expected to be 500 mg based on animal toxicology studies and human PK predictions for LY3154885, CCI

CCI A 500-mg dose in humans is predicted to result in a mean plasma AUC of CCI $\mu\text{g}\cdot\text{hr}/\text{mL}$ and C_{\max} of CCI $\mu\text{g}/\text{mL}$; these values are equivalent to 1/10th the AUC at the NOAEL in monkeys and 1/10th the C_{\max} at the NOAEL in rats. The C_{\max} and AUC-based multiples associated with CCI from the non-GLP study in rats, which were not observed at similar exposures in the GLP study, are also presented in Table HUAA.5.1. To note, the predicted human C_{\max} at 500 mg is CCI below the C_{\max} at the NOEL for PPD in both rats and monkeys. Pharmacokinetic data will be reviewed during the study to support dose escalations (see Section 10.3.5 for details) and maintain predicted drug exposures below 1/10th the AUC at the NOAEL in monkeys and 1/10th the C_{\max} at the NOAEL in rats. A dose higher than 500 mg may be studied if human PK data from previous cohorts suggests the predicted exposure will be below 1/10th the AUC at the NOAEL in monkeys and 1/10th the C_{\max} at the NOAEL in rats.

In Part B (CYP3A4 Interaction), the LY3154885 dose selection will be based on emerging data from Part A but is currently planned to be ≤ 200 mg. It is predicted that the maximum exposure increase in LY3154885 when administered with itraconazole, a strong CYP3A4 inhibitor, is

approximately 2.6-fold. Therefore, the LY3154885 dose selected will be below the highest dose deemed well tolerated that has a plasma exposure to allow for up to a 2.6-fold increase in exposure that may result from coadministration with itraconazole, and the predicted LY3154885 plasma exposure at this dose when coadministered with itraconazole will be below 1/10th the AUC at the NOAEL in monkeys and 1/10th the C_{max} at the NOAEL in rats. The dose regimen for itraconazole will be 200 mg twice daily on Day 8 (dose separated by 12 hours) and once daily on Days 9 through 17.

[figure not shown]
In Part C (MAD), the doses will be based on emerging safety, tolerability, and PK data from Part A (SAD) and Part B. Emerging safety and tolerability data from Part C will also be considered for dose escalation. The highest dose tested in Part C will not exceed the highest dose in Part A (currently planned to be 500 mg) that was well tolerated or the maximum exposure achieved in Part A or B found to be well tolerated.

In Part D, the planned dose for the capsule and tablet will be ≤ 400 mg but will ultimately be based on emerging safety, tolerability, and PK data from Part A.

CCI

CCI

6. Study Population

Eligibility of subjects for the study will be based on the results of screening medical history, physical examination, vital signs, clinical laboratory tests, and ECG. The nature of any conditions present at the time of the physical examination and any preexisting conditions will be documented.

Screening may occur up to 28 days prior to enrollment. Subjects who are not enrolled within 28 days of screening may be subjected to an additional medical assessment and/or clinical measurements to confirm their eligibility.

Prospective approval of protocol deviations to recruitment and enrollment criteria, also known as protocol waivers or exemptions, are not permitted.

6.1. Inclusion Criteria

Subjects are eligible for inclusion in the study only if they meet all of the following criteria at screening:

- [1] are overtly healthy males or females, as determined by medical history and physical examination

- [1a] male subjects:

Men, regardless of their fertility status, with partners who are nonpregnant women of childbearing potential, must agree to either remain abstinent (if this is their preferred and usual lifestyle) or use condoms with spermicide as well as 1 additional highly effective (<1% failure rate) method of contraception (such as combination oral contraceptives, implanted contraceptives, or intrauterine devices) or effective method of contraception (such as diaphragms with spermicide) for 3 months following dosing.

Men with pregnant partners should use condoms with spermicide during intercourse for the duration of the study or for 3 months following dosing, whichever is longer.

Men who are in exclusively same-sex relationships (as their preferred and usual lifestyle) or with female partners of nonchildbearing potential are not required to use contraception.

Men should refrain from sperm donation for the duration of the study or for 3 months following the last dose of study drug, whichever is longer.

- [1b] female subjects of nonchildbearing potential, including those who are:

- A. infertile due to surgical sterilization (hysterectomy, bilateral oophorectomy, bilateral salpingectomy, confirmed tubal ligation, or tubal occlusion) or congenital anomaly such as Müllerian agenesis; or
 - B. postmenopausal, defined as 1 of the following:

- i. a woman at least 50 years of age with an intact uterus, not on hormone replacement therapy, who has had either:
 - a. cessation of menses for at least 1 year; or
 - b. at least 6 months of spontaneous amenorrhea with a follicle-stimulating hormone level ≥ 40 mIU/mL at screening
- ii. a woman at least 55 years of age, not on hormone replacement therapy, who has had at least 6 months of spontaneous amenorrhea; or
- iii. a woman at least 55 years of age with a diagnosis of menopause prior to starting hormone replacement therapy

- [2] are between 21 and 65 years of age, inclusive, at the time of screening
- [3] have a body mass index (BMI) of 18.0 to 35.0 kg/m², inclusive
- [4] have clinical laboratory test results within normal reference range for the population or investigative site, or results with acceptable deviations that are judged to be not clinically significant by the investigator
- [5] have venous access sufficient to allow for blood sampling per the protocol
- [6] are reliable and willing to make themselves available for the duration of the study and are willing to follow study procedures
- [7] are able and willing to give signed informed consent approved by Lilly and the ethical review board (ERB) governing the site

6.2. Exclusion Criteria

Subjects will be excluded from study enrollment if they meet any of the following criteria at screening and/or enrollment:

- [8] are investigative site personnel directly affiliated with this study and their immediate families. Immediate family is defined as a spouse, biological or legal guardian, child, or sibling
- [9] are Lilly employees
- [10] are currently enrolled in a clinical study involving an investigational product or any other type of medical research judged not to be scientifically or medically compatible with this study
- [11] have participated, within the last 30 days, in a clinical study involving an investigational product. If the previous investigational product has a long half-life, 5 half-lives or 30 days (whichever is longer) should have passed
- [12] have previously completed or withdrawn from this study or any other study investigating LY3154885, and have previously received LY3154885
- [13] have known allergies to LY3154885, related compounds or any components of the formulation, itraconazole, or history of significant atopy

- [14] have an abnormality in the 12-lead ECG that, in the opinion of the investigator, increases the risks associated with participating in the study
- [15] have a marked baseline prolongation of corrected QT (QTc) interval (for example, repeated demonstration of a QTcB interval >450 msec for males or >470 msec for females);
 - A history of additional risk factors for Torsades de Pointes (for example, heart failure, hypokalemia, family history of Long QT Syndrome);
 - The use of concomitant medications that prolong the QT/QTc interval
- [16] have an abnormal BP (taken after the subject has been in a supine position for at least 5 minutes) for the population, as determined by a systolic BP >140 mm Hg or a diastolic BP >90 mm Hg at screening or a preexisting history of hypertension. Up to 2 additional measurements may be taken after an appropriate resting interval at screening to confirm eligibility
- [17] have a significant history of or current cardiovascular, respiratory, hepatic, renal, gastrointestinal, endocrine (such as Cushing syndrome, hyperthyroidism, hyperaldosteronism), hematological, or neurological disorders capable of significantly altering the absorption, metabolism, or elimination of drugs; of constituting a risk when taking the investigational medicinal product (IMP); or of interfering with the interpretation of data
- [18] have a history of or current significant psychiatric disorders
- [19] have a history of head injury (eg, skull fracture, cerebral contusion, trauma resulting in prolonged unconsciousness), intracranial neoplasm or hemorrhage, prior seizure (other than remote history of childhood febrile seizure), or other condition that would place the subject at increased risk of seizure
- [20] regularly use known drugs of abuse and/or show positive findings on drug screening
- [21] show evidence of human immunodeficiency virus (HIV) infection and/or positive human HIV antibodies
- [22] show evidence of hepatitis B and/or positive hepatitis B surface antigen
- [23] show evidence of hepatitis C and/or positive hepatitis C antibody
- [24] are women who are lactating

- [25] have used or intend to use over-the-counter/herbal supplements (eg, St. John's wort) or prescription medication within 14 days or 5 half-lives, whichever is longer, before initial dosing or during the study (vitamin/mineral supplements and occasional paracetamol/acetaminophen up to 3-g dose in a 24-hour period are allowed). If this situation arises, inclusion of an otherwise suitable subject may be at the discretion of the investigator and sponsor. Medications that inhibit or induce CYP3A4 are specifically excluded within 14 days prior to dosing and during the study
- [26] have donated blood of more than 450 mL or have participated in a clinical study that required similar blood volume drawn within the past 3 calendar months
- [27] have an average weekly alcohol intake that exceeds 21 units per week (males up to age 65) and 14 units per week (males >65 years and females) or are unwilling to stop alcohol consumption for 24 hours prior to CRU admissions until the completion of each study period (1 unit = 12 oz or 360 mL of beer; 5 oz or 150 mL of wine; 1.5 oz or 45 mL of distilled spirits)
- [28] have tobacco consumption of more than 10 cigarettes per day (or the equivalent) or are unable or unwilling to refrain from nicotine use while resident at the CRU
- [29] consume Seville oranges or Seville orange-containing products, grapefruit or grapefruit-containing products, star fruits or star fruit-containing products, pomegranates, and/or pomelos within 14 days prior to dosing or during the study
- [30] in the opinion of the investigator or sponsor, are unsuitable for inclusion in the study

In addition, for Part B only:

- [31] have impaired hearing or a history of hearing problems

In addition, for Part C only:

- [32] Presence of significant uncontrolled neuropsychiatric disorder; have recent history (within 30 days prior to the screening visit and any time between screening and admission) of a suicide attempt; or develops active suicidal ideation with some intent to act with or without a specific plan (yes to question 4 or 5 on the "Suicidal Ideation" portion of the Columbia Suicide-Severity Rating Scale [C-SSRS]) or develops suicide-related behaviors as recorded on the C-SSRS at screening or admission; or are clinically judged by the investigator to be at risk for suicide

6.2.1. Rationale for Exclusion of Certain Study Candidates

Exclusion Criteria [8] and [9] prevent conflict of interest in study participants. Exclusion Criteria [10] through [29] and [32] exclude medical conditions, medication intolerance, and concomitant medication use that may constitute a risk for the subject and/or may confound the

assessment of study endpoints. Exclusion Criterion [31] excludes subjects with hearing problems in Part B because itraconazole has been associated with transient or permanent hearing loss.

6.3. Lifestyle and/or Dietary Requirements

Throughout the study, subjects may undergo medical assessments and review of compliance with requirements before continuing in the study.

6.3.1. Meals and Dietary Restrictions

Part A: Subjects will be required to fast overnight (at least 8 hours) prior to dosing on Day 1 and for at least 4 hours after dosing with LY3154885/placebo, with the exception of water, which will be freely available after dosing.

Part B: Subjects will be required to fast overnight (at least 8 hours) prior to each dosing day (including itraconazole dosing) and for at least 4 hours after dosing with LY3154885, and coadministration of LY3154885 and itraconazole, with the exception of water that will be freely available after dosing. Subjects will also need to fast for approximately 2 hours prior to the evening dose of itraconazole on Day 8 and at least 1 hour after dosing, with the exception of water, which will be freely available after dosing.

Part C: Subjects will be required to fast overnight (at least 8 hours) on all dosing days and for at least 4 hours after dosing on Days 1, 7, and 14 (intensive PK days), with the exception of water, which will be freely available after dosing. On nonintensive PK days, subjects may receive a light breakfast approximately 1 hour after dosing.

Part D: In Periods 1 and 2, subjects will be required to fast overnight (at least 8 hours) prior to dosing on Days 1, 8, and 14 and for at least 4 hours after dosing with LY3154885, with the exception of water, which will be freely available after dosing. All other meals will be provided according to CRU procedures. In Period 3, following an overnight fast of at least 8 hours, subjects will start the high-fat diet (see below) 30 minutes prior to administration of the study drug on Days 1, 8, and 14. Subjects will consume this entire meal in 30 minutes or less; however, the study drug will be administered 30 minutes after the start of the meal. The study drug should be administered with approximately 240 mL of room temperature water. No further food will be allowed for at least 4 hours postdose. Fluids will be restricted from 1 hour prior to and until 1 hour after dosing, except for fluid provided with the meal and water required for dose administration.

The standardized high-fat, high-calorie meal (fat comprises approximately 50% of total caloric content of the meal) should consist of approximately 1000 calories. No additional food or substitute is allowed. A typical test meal is 2 eggs fried or scrambled in butter, 2 strips of bacon, 2 slices of toast with butter, 4 ounces of hash brown potatoes, and 8 ounces of whole milk. This test meal derives approximately 150, 250, and 500 to 600 calories from protein, carbohydrates, and fat, respectively.

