7.1. Treatment Administered

This study involves a comparison of LY3154885 or matching placebo administered orally. [Table HUAA.7.1](#) shows the treatment regimens.

Capsules (or tablets for optional Part D) of LY3154885 and/or placebo will be administered orally with approximately 240 mL of room temperature water in the morning of each dosing day with subjects in a sitting position. Subjects will not be allowed to lie supine for approximately 2 hours after dosing, unless clinically indicated or for study procedures.

Table HUAA.7.1. Treatments Administered

Treatment Name	LY3154885	LY3154885	Placebo	Itraconazole
Dosage Formulation	Capsule	Tablet	Capsule	Solution
Unit Dose Strength(s)/ Dosage Level(s)	Extemporaneous preparation 15 to 500 mg	Extemporaneous preparation Dose to be determined	Matching placebo	10 mg/mL
Route of Administration	Oral	Oral	Oral	Oral

The investigator or designee is responsible for:

- explaining the correct use of the investigational product(s) to the subject
- verifying that instructions are followed properly
- maintaining accurate records of investigational product dispensing and collection
- returning all unused medication to Lilly or its designee at the end of the study

Note: In some cases, sites may destroy the material if, during the investigative site selection, the evaluator has verified and documented that the site has appropriate facilities and written procedures to dispose of clinical materials.

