Effect of formulation: The AUC and C_{max} for LY3154885 following administration with a capsule and tablet formulation in a fasted state will be log transformed and analyzed using a mixed effects ANOVA model. The model will include fixed effects for formulation (capsule : tablet). The LS means for each formulation and the 90% CI for the difference in means will be estimated from the ANOVA model and back-transformed from the log scale to provide estimates of the geometric means and 90% CIs for the ratio of the means. The t_{max} of LY3154885 between formulations will be analyzed using a Wilcoxon signed-rank test. An estimate of the median difference and 90% CI will be calculated.

Effect of high-fat diet: The AUC and C_{max} for LY3154885 following administration with a tablet formulation in the fed state and fasted state will be log transformed and analyzed using a mixed-effects ANOVA model. The model will include fixed effects for food (fed : fasted). The LS means for fed and fasted and the 90% CI for the difference in means will be estimated from the ANOVA model and back-transformed from the log scale to provide estimates of the geometric means and 90% CIs for the ratio of the means. The t_{max} of LY3154885 between fed and fasted will be analyzed using a Wilcoxon signed-rank test. An estimate of the median difference and 90% CI will be calculated.

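### Part D: in the first hour after dosing the fed and fasted tablet periods follow different water rules, so the food-effect ratio may include a fluid effect that the analysis cannot separate from food

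*Protocol*

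**What the plan says.** Protocol Section 5.1.4 assigns the capsule to Period 1, the fasted tablet to Period 2 and the tablet after a high-fat meal to Period 3. Section 6.3.1 sets the dietary rules for Part D in one paragraph:

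- **Periods 1 and 2 (fasted).** Subjects fast overnight and for at least 4 hours after dosing, "with the exception of water, which will be freely available after dosing. All other meals will be provided according to CRU procedures".
- **Period 3 (fed).** After an overnight fast, the meal starts 30 minutes before dosing. "The study drug should be administered with approximately 240 mL of room temperature water". No more food is allowed for at least 4 hours. "Fluids will be restricted from 1 hour prior to and until 1 hour after dosing, except for fluid provided with the meal" and for the water taken with the dose.

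Section 7.1 applies the same dosing-water volume to capsules and tablets alike: "administered orally with approximately 240 mL of room temperature water in the morning of each dosing day". The typical test meal in Section 6.3.1 includes "4 ounces of hash brown potatoes, and 8 ounces of whole milk".

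Under Protocol Section 10.3.2.2, AUC and Cmax "following administration with a tablet formulation in the fed state and fasted state" are compared on the log scale with food as the only stated fixed effect. SAP Section 9.3.2 adds a random subject effect. Both analyse tmax with a Wilcoxon signed-rank test. The Part D Schedule of Activities places PK samples at predose, 0.5 and 1 hour and later, on Days 1, 8 and 14 of each period.

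**The concern.** The secondary objective is the effect of a high-fat diet on Cmax, tmax and AUC. For the fed/fasted ratio to answer that question, the meal should be the only planned difference between Periods 2 and 3. Here a second stated condition, access to water just after dosing, changes at the same moment and in the same subjects. By restricting fluids in Period 3, the protocol treats fluid around dosing as worth controlling, but it leaves the reference period without that control.

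If water taken soon after the dose altered early absorption of this tablet, the change would be reported as a food effect. The Part D schedule lists no record of water intake, so the question could not be examined afterwards.

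**Working it through.** The plan states no figure on this point, so the check is a comparison of text followed by a calculation for scale.

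**Step 1. The two rules by time window.** Sources: Protocol Sections 6.3.1 and 7.1.

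| Window | Period 2, fasted tablet | Period 3, fed tablet | Same? |
|---|---|---|---|
| 1 h before dosing to dosing | Overnight fast; no fluid rule stated | Restricted, except meal fluid | Rule stated for Period 3 only |
| At dosing | About 240 mL water | About 240 mL water | Yes |
| Dosing to 1 h after | Water unrestricted | Restricted | **No** |
| After 1 h | Water unrestricted | Restriction has ended | No stated difference |

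The firm difference is the third row. The milk in the typical meal, 8 × 29.57 mL ≈ 237 mL, belongs to the fed condition itself and is not part of the discrepancy.

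**Step 2. Which periods the restriction covers.** The sentence follows the Period 3 instructions and refers to fluid served with the meal, and only Period 3 is dosed with a meal. Read as covering all of Part D, it would contradict the phrase "with the exception of water, which will be freely available after dosing" in the same paragraph. The paragraph needs reconciling on either reading. The Part D schedule, Sections 5.1.4, 7.1 and 10.3.2.2 of the protocol, and SAP Sections 5.4 and 9.3.2 do not align the rules.

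**Step 3. Can the analysis separate the two?** No. Every fed observation carries one rule and every fasted tablet observation the other. A fluid-rule term would be identical to the food term and could not be estimated alongside it. The signed-rank test on tmax has the same limitation. Varying the order of the periods would not help, because the rule follows the fed condition.

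**Step 4. Where it would show.** The 0.5 h sample falls inside the window and the 1 h sample at its edge, so early concentrations, and through them Cmax and tmax, are the most exposed.

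**Step 5. Scale, on assumptions.** The documents give no intake volumes, no effect of water on exposure and no within-subject variability.

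- Suppose the fluid rule multiplies the fed/fasted ratio by f. Then observed ratio = true ratio × f. With f assumed between 0.90 and 1.10, a true ratio of 1.00 is reported as 0.90 to 1.10.
- For comparison, the 90% CI of a paired log-scale ratio extends by the factors exp(±t(0.95, n−1) × s_w × √(2/n)), where s_w = √ln(1 + CV²). Take n = 9 (Protocol Section 5.2), t(0.95, 8) = 1.860, √(2/9) = 0.471, and one dose per period.
 - CV 15%: s_w = 0.149; 1.860 × 0.149 × 0.471 = 0.131; factors 0.88 to 1.14.
 - CV 40%: s_w = 0.385; 1.860 × 0.385 × 0.471 = 0.338; factors 0.71 to 1.40.
- The plan does not say how Days 1, 8 and 14 are combined. If all three doses were averaged with independent errors, √(2/9) becomes √(2/27), and the factors narrow to 0.927–1.078 (CV 15%) and 0.823–1.215 (CV 40%).

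On the single-dose calculation, a 10% distortion stays within the CI's half-width across this CV range. With three doses averaged and a CV of 15%, it would exceed it.

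**The case against.** The strongest reply is that the two rules differ on paper with little practical effect. Several parts of it stand.

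- **Free water permits drinking but does not require it.** A reader might infer that the food-effect ratio definitely contains a fluid-intake difference. The documents do not support that: they plan no fasted intake volume, and actual intake could be small.
- **The firm difference lasts one hour.** A reader might infer contrary rules on both sides of dosing. Before dosing, the fasted text is silent, and since the only water exception it states is postdose, it can even be read as allowing none.
- **The mechanism is not documented.** It is tempting to argue that extra water speeds dissolution of a lipophilic drug. Protocol Section 3.2 also describes acceptable solubility and high permeability, and nothing in either document links water after a 240 mL dose to exposure. The direction of any effect is equally unknown.
- **Gastric contents differ by design.** The meal supplies about 1000 calories and some fluid, so equal water rules would not make the two stomachs alike. That difference belongs to the food effect being measured; the postdose water rule does not.
- **The stakes are low.** Part D is optional, its food evaluation is a pilot (Section 5.1), the study is not powered for hypothesis tests (Section 10.1), and the plan states no boundary for declaring no food effect.

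What does not stand is that these limits make the difference harmless. A wide interval describes random error. It is no reason to keep a systematic difference between conditions that one sentence would remove.

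**Conclusion.** The point holds as a low-priority improvement. In the first postdose hour the stated fluid rule differs between the fed and fasted tablet periods, and the predose restriction is stated for Period 3 only. The fed/fasted ratio may therefore reflect the meal together with a different fluid rule, and no planned or added model term can separate the two.

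The size and direction of any effect cannot be derived from the documents, and it may be negligible. The 0.90 to 1.10 range used for scale is an assumption, as are the CVs of 15% to 40%.

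A reader might go further and infer that the effect cannot average out because all subjects and all three dosing days share it. The rule is indeed common to every fed/fasted pair, but a persistent bias also requires that water be drunk and that it affect exposure in a consistent direction. The documents establish neither. The capsule–tablet comparison is unaffected, since Periods 1 and 2 share one rule.

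**What to change.** Reconcile the two statements in Protocol Section 6.3.1 so that one identical fluid rule around dosing, before and after, applies to at least Periods 2 and 3, with fluid in the test meal as the only exception. If the Period 2 rule changes, change Period 1 with it so that the capsule–tablet comparison stays matched. Which rule to adopt is the sponsor's choice. The dosing-water volume needs no change.

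The cost is one sentence, with no effect on sample size, visits or analysis. If the Period 3 rule is extended, fasted subjects go briefly without water, and fasted dosing in Part D no longer matches the free-water rule that Section 6.3.1 sets for Parts A to C. If the text is left as it is, the study report should state that the fed/fasted ratio reflects the meal together with a different fluid rule.
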